Sponsor:	Menlo Therapeutics Inc.
Study Centers:	Approximately 45 sites in the USA and UK
Development Phase:	Phase 2
Study Objectives:	
The primary objective of this study is to assess the effectiveness of serlopitant for the treatment of refractory chronic cough after 12 weeks of treatment in reducing 24-hour objective cough frequency.
 
The secondary objectives are as follows:
 
 • To evaluate the effectiveness of serlopitant as compared to placebo after 4 and 8 weeks of treatment in reducing 24-hour objective cough frequency • To evaluate the effectiveness of serlopitant as compared to placebo after 4, 8 and 12 weeks of treatment in reducing awake objective cough frequency • To evaluate the effectiveness of serlopitant as compared to placebo after 4, 8 and 12 weeks of treatment in reducing sleep objective cough frequency • To evaluate the effectiveness of serlopitant in: 
 ◦ Reducing the cough severity measured by a Visual Analog Scale (VAS) ◦ Improving cough-specific quality of life (LCQ) • To assess the safety and tolerability of repeated oral doses of serlopitant in subjects with treatment refractory chronic cough
Study Design:	
This is a 12-week randomized, parallel-group, double-blind, placebo-controlled study of serlopitant in subjects with treatment refractory chronic cough.
 
Approximately 170 subjects who meet entry criteria will be randomly assigned to serlopitant 5 mg or matching placebo in a 1:1 ratio for up to 84 days. The randomization will be stratified by country and gender.
 
The study will consist of three periods, for a total study period of approximately 18 weeks:
 
 • Screening period: 14 days • Treatment period: 84 days • Follow-up period: 28 days 
During the screening period, subjects will undergo eligibility evaluations. Subjects must be willing to comply with restrictions on allowable concomitant therapies for the duration of the study.
 
At the Baseline visit, eligible subjects will be randomly assigned to one of two treatment groups and will have baseline cough monitoring conducted. One day after the Baseline visit, subjects will take a loading dose (3 tablets taken orally) in the morning on the first day of the treatment period (Study Day 1). Starting

	
on Study Day 2, subjects will take one tablet per day taken orally in the morning. Subjects will be instructed to take all doses at approximately the same time each day and no sooner than 2 hours before or after a meal.
 
The primary efficacy endpoint will be assessed at Day 84 of treatment.
 
After completion of the 84-day treatment period, all subjects will enter a 28-day follow-up period. Subjects who discontinue treatment early at any time during the treatment period will have an Early Treatment Discontinuation (ETD) visit within 7 days after their last dose of study drug in addition to a follow-up visit.

Planned Sample Size:	Approximately 170 subjects will be randomized.
Study Population:	
The study will consist of adults with a history of treatment refractory chronic cough.
 
Inclusion Criteria:
 
Subjects who meet all of the following criteria will be included in the study:
 
 1. Female and males between 18 and 80 years of age inclusive, at Screening 2. Chest radiograph or computed tomography (CT) Thorax within the last 5 years not demonstrating any abnormality considered to be significantly contributing to the chronic cough in the opinion of the Principal Investigator and Menlo Therapeutics Medical Monitor 3. Have a diagnosis of treatment refractory chronic cough or unexplained cough for at least one year (see American College of Chest Physicians/British Thoracic Society (ACCP/BTS) guidelines in Appendix C) 4. At Screening have a score of ≥ 40mm on the Cough Severity VAS 5. At Baseline (Day 0) have a score of ≥ 40mm on the Cough Severity VAS 6. All female subjects who are of childbearing potential must practice highly effective contraception (i.e., pregnancy prevention method with a failure rate of $< 1\%$ per year) from the time of the initial screening visit until 4 weeks after last dose of study drug. Please refer to Section 7.1.5 for acceptable methods of contraception 7. Have provided written informed consent 8. Are willing and able to comply with all aspects of the protocol 
Exclusion Criteria:
 
 1. Prior treatment with serlopitant or other neurokinin-1 receptor (NK₁-R) antagonists (e.g., aprepitant, orvepitant) 2. Current smoker or individuals who have given up smoking within the past 12 months 3. FEV1/FVC $< 60\%$ 4. Body mass index (BMI) < 18 kg/m² or ≥ 40 kg/m² at Screening 5. History of upper or lower respiratory tract infection or recent significant change in pulmonary status within 4 weeks of the Baseline Visit (Day 0) 6. History of cystic fibrosis 7. History of opioid use within 1 week of the Baseline Visit (Day 0)

	
 8. Requiring concomitant therapy with prohibited medications (see Section 5.7) 9. Treatment with biologic therapies within 8 weeks or 5 half-lives prior to the Baseline Visit (Day 0), whichever is longer 10. Treatment with strong CYP3A4 inhibitors within 4 weeks prior to the Baseline Visit (Day 0) (see Appendix B) 11. Treatment with any investigational therapy within 4 weeks (investigational biologic therapies within 8 weeks) prior to the Baseline Visit (Day 0) 12. Serum creatinine, total bilirubin, alanine aminotransferase (ALT) or aspartate aminotransferase (AST) > 2x the upper limit of normal (ULN) during screening 13. Positive test for any drug of abuse 14. History of malignancy within 5 years prior to the Baseline Visit (Day 0), with the exception of completely treated and non-metastatic basal cell carcinoma or squamous cell carcinoma of the skin 15. Any known psychiatric diagnosis meeting DSM-5 criteria which may confound the assessment of serlopitant safety or efficacy, or interfere with the subject's ability to comply with protocol-mandated activities, within 3 years prior to randomization. Examples of such DSM-5 diagnoses include but are not limited to major depressive disorder, bipolar disorder, schizophrenia, psychotic disorder, intellectual disability, severe alcohol use disorder. 16. Known active hepatitis infection 17. Known history of human immunodeficiency virus (HIV) infection 18. History of hypersensitivity to serlopitant or any of its components 19. Currently pregnant or breastfeeding female subject 20. Females of childbearing potential who are unable or unwilling to practice highly effective contraception (pregnancy prevention) 21. Presence of any medical condition or disability that, in the investigator's opinion, could interfere with the assessment of safety or efficacy in this trial or compromise the safety of the subject, including clinically significant ECG abnormalities during screening 22. Planned or anticipated major surgical procedure or other activity that would interfere with the subject's ability to comply with protocol-mandated assessments (e.g., extended international travel) during the subject's participation in the study
Study Drug:	Serlopitant 5 mg oral tablets and matching placebo.
Dosage:	
Serlopitant: 5 mg once daily by mouth for 84 days, following a 3-tablet loading dose on the first day of the treatment period.
 
Matching placebo: Once daily by mouth for 84 days, following a 3-tablet loading dose on the first day of the treatment period.

Prohibited Concomitant Therapy
	
The following therapies are excluded from 1 week prior to the Baseline Visit (Day 0) through the follow-up period:
 
• Opioids (including codeine). Opioids (including codeine), if required for other indications, are permitted provided that subjects are receiving a stable dose for at least one week prior to the Baseline Visit (Day 0) and still experiencing a troublesome cough. Subjects must remain on a stable dose for the duration of the treatment period. 
The following cough therapies are excluded from 2 weeks prior to the Baseline Visit (Day 0) through the end of the treatment period:
 
• Dextromethorphan• Guaifenesin• Chlorpheniramine maleate extended release tablets• Benzonatate 
The following therapies are excluded from 2 weeks prior to the Baseline Visit (Day 0) through the follow-up period:
 
• Pregabalin, gabapentin, thalidomide, or amitriptyline for the treatment of cough. Pregabalin, gabapentin, thalidomide, or amitriptyline if required for other indications, is permitted if subjects are receiving a stable dose and still experiencing a troublesome cough. Subjects must remain on a stable dose for the duration of the treatment period. 
The following therapies are excluded from 4 weeks prior to the Baseline Visit (Day 0) through the follow-up period:
 
• Systemic immunosuppressive/immunomodulatory therapies (including but not limited to PDE4 inhibitors, cyclosporine, mycophenolate-mofetil, methotrexate, azathioprine, or phototherapy)• Strong CYP3A4 inhibitors (See Appendix B)• Any investigational therapy 
The following therapies are excluded from 8 weeks prior to the Baseline Visit (Day 0) through the follow-up period:
 
• Biologic therapies• Investigational biologic therapies 
The following therapy is excluded from 12 weeks prior to the Baseline Visit (Day 0) through the follow-up period:
 
• Treatment with an ACE-inhibitor
---------------------------------------	---


Primary Efficacy Endpoint:
	
The primary efficacy endpoint is: Change from Baseline in 24-hour objective cough frequency after 12 weeks (Day 84) of treatment.

Secondary Efficacy Endpoints:
	
Key Secondary
 
 • Change from Baseline in awake objective cough frequency after 12 weeks (Day 84) of treatment • Proportion of subjects with $\geq 30\%$ reduction in 24-hour objective cough frequency per hour at Week 12 (Day 84) • Proportion of subjects with $\geq 30\%$ reduction in awake objective cough frequency per hour at Week 12 (Day 84) • Change from Baseline in Cough Severity Visual Analog Scale (VAS) at Week 12 (Day 84) 
Other Secondary
 
 • Change from Baseline in 24-hour objective cough frequency after 4 and 8 weeks (Days 28 and 56) of treatment • Change from Baseline in awake objective cough frequency after 4 and 8 weeks (Days 28 and 56) of treatment • Change from Baseline in 24-hour objective cough frequency at the Follow-Up visit (Day 112) • Change from Baseline in sleep objective cough frequency after 4, 8 and 12 weeks (Days 28, 56 and 84) of treatment • Change from Baseline in Cough Severity Visual Analog Scale (VAS) at Weeks 4 and 8 (Days 28 and 56) • Change from Baseline in Leicester Cough Questionnaire (LCQ) individual Domain and Total scores • Patient's Global Impression of Change (PGIC) • Clinician's Global Impression of Change (CGIC)

Safety Endpoints:
	
Safety Assessments
 
Safety will be assessed through monitoring of adverse events (AEs), physical examinations (including vital signs), electrocardiograms (ECGs), and laboratory tests. Safety assessment frequency is shown in the Schedule of Assessments and Procedures.
 
Safety endpoints include the following:
 
 • Incidence of treatment-emergent adverse events (TEAEs) and serious adverse events (SAEs) • Change in clinical laboratory parameters following study drug exposure • Changes in vital sign and ECG parameters following study drug exposure • Plasma concentrations of serlopitant and metabolites


Decision Rule and Sample Size
	
A total of 170 subjects (85/arm) in 1:1 ratio of serlopitant 5 mg or placebo will provide 90% power to detect a 25% relative reduction (placebo-adjusted ratio of 0.75) in 24-hour objective cough frequency or awake objective cough frequency using a two-sample t-test at a one-sided significance level of 0.05. This assumes that 24-hour cough frequency or awake cough frequency follows a log-normal distribution with a CV of 0.64. This sample size also considers an expected dropout rate of 15%.
 
The comparisons related to the primary and key secondary objectives will be done in a hierarchical manner to control the familywise error rate. The testing procedure will start by testing the primary endpoint and then proceed to the key secondary endpoints by following the order as specified in Section 8.9.4.

Analysis Sets:
	
Efficacy Analysis Sets
 
Full Analysis Set (FAS)– All randomized subjects who have taken at least one dose of study medication and provided at least one baseline and at least one post-baseline primary endpoint observation during the treatment period. Participants will be analyzed according to the treatment group to which they are randomized.
 
Safety Analysis Sets
 
The safety analysis set will consist of all subjects randomized who receive at least one dose of study medication. Subjects will be classified based upon the treatment received.
 
PK Analysis Set
 
The PK analysis set will consist of all subjects who receive ≥ 1 dose of serlopitant and who have at least 1 post-dose PK blood sample available for analysis.


Statistical Methods:
	
Efficacy Analyses:
 
The FAS population will serve as the primary population for the analysis of efficacy data in this study.
 
The primary efficacy endpoint of this study is change from Baseline in 24-hour objective cough frequency after 12 weeks (84 days) of treatment.
 
As the change in 24-hour cough frequency may have a skewed and wide distribution, the primary analysis for the primary endpoint will be analyzed on the natural log scale. The difference between serlopitant (5 mg) and placebo will be estimated using a mixed effect repeated measures (MMRM) model. The model will include factors for treatment, visit, country, sex, the interaction of treatment by visit; and the log-transformed baseline value as a covariate. The MMRM model will use all available 24-hour cough frequency data on Day 28, 56, and 84. The geometric mean of the 24-hour coughs per hour will be presented by treatment and by visit. The percent difference change between serlopitant and placebo will be estimated by $100*(e^{diff} - 1)$, where diff is the difference provided by the analysis of the log transformed variable.
 
In order to evaluate the robustness of efficacy results and assess the effect of missing data, additional sensitivity analyses for the primary efficacy variables will be employed.
 
Safety Analyses:
 
The incidence of all AEs and treatment-related AEs will be tabulated by treatment received. These AEs will be classified by system organ class and preferred term using the Medical Dictionary for Regulatory Activities (MedDRA). For incidence reporting, if a subject reported more than one AE that was coded to the same system organ class or preferred term, the subject will

	
be counted only once for that specific system organ class or preferred term. An overview of AEs, which includes subject incidence of AEs, treatment-related AEs, AEs by severity, SAEs, deaths, and AEs leading to discontinuation, will be presented.
 
Clinical safety laboratory values will be measured by a central laboratory. Summary statistics for actual values and for changes from Baseline will be tabulated for laboratory results by scheduled visit.
 
Subjects with clinical laboratory values outside of the normal reference range at any post-baseline assessment will be summarized. Shifts from Baseline laboratory values will be tabulated.
 
The observed vital signs and ECG data and change from Baseline for each measurement day will be summarized with descriptive statistics.

Expected Duration of Subject's Participation	Approximately 126 days: 14 days of screening, 84 days of treatment, and a follow-up period of 28 days.

This study will be conducted in accordance with the Guidelines of Good Clinical Practices (GCPs).

TABLE OF CONTENTS

CLINICAL STUDY PROTOCOL	1
SIGNATURE PAGE FOR INVESTIGATOR(S)	2
SPONSOR PROTOCOL APPROVAL SIGNATURE(S).....	3
PROTOCOL SYNOPSIS	4
TABLE OF CONTENTS.....	11
LIST OF APPENDICES.....	14
LIST OF FIGURES	14
LIST OF TABLES	14
LIST OF ABBREVIATIONS AND DEFINITIONS OF TERMS.....	15
1 INTRODUCTION	16
1.1 Refractory Chronic Cough.....	16
1.2 Substance P and the Neurokinin-1 Receptor in Cough.....	16
1.3 Serlopitant.....	17
1.3.1 Serlopitant Background	17
1.3.2 Serlopitant Clinical Data in Phase 1 and Non-Pruritus Studies.....	17
1.3.3 Serlopitant in Pruritus-Related Studies.....	18
1.3.4 Serlopitant in Chronic Cough	19
2 STUDY OBJECTIVES.....	19
3 STUDY DESIGN.....	19
3.1 Overall Study Design.....	19
3.2 Rationale for Study Design and Dose Selection.....	20
3.3 Study Endpoints.....	21
3.3.1 Primary Efficacy Endpoint	21
3.3.2 Key Secondary Efficacy Endpoints	21
3.3.3 Additional Secondary Efficacy Endpoints.....	21
3.3.4 Safety Endpoints.....	22
3.4 Safety Review	22
3.4.1 Safety Monitoring Team.....	22
4 SELECTION OF STUDY POPULATION	22
4.1 Study Population.....	22
4.2 Inclusion Criteria	23
4.3 Exclusion Criteria	23
5 STUDY DRUG.....	25
5.1 Study Drug Supply, Route of Administration, and Storage.....	25
5.2 Labeling and Study Drug Accountability	25
5.3 Dosing Regimen.....	25
5.4 Dose Modification	25

5.5	Missed or Delayed Doses.....	25
5.6	Study Drug Discontinuation	26
5.7	Concomitant and Excluded Therapies	26

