8.3 Derivations of Efficacy Variables

The 24-hour cough frequency (coughs per hour) for a specified visit is calculated as:

24-hour cough frequency = (total number of cough events during the monitoring period (24-hour interval))/24

The awake cough frequency (coughs per hour) is defined as below:

Awake cough frequency = (total number of cough events during the monitoring period (24-hour interval) the subject is awake)/(Total duration (in hours) for the monitoring period the subject is awake)

Awake duration (hours) is time between waking up and sleep during the 24-hour monitoring period.

The cough data will contain all cough events occurring during that 24-hour monitoring period as well as the information about “sleep time” and “awake time”. Any session with duration of recording < 4 hours will be considered as missing.

In general, each 24-hour session is composed by an awake monitoring period and a sleep monitoring period. If a subject did not wake up before the end of the recording session, it will be assumed that the subject slept for the rest of the session. The session will have missing awake time, and the rest of session will be considered under the sleep monitoring period. For any session with both sleep time and awake time missing, the entire 24-hour session will be considered under the awake monitoring period, unless the session has early termination of recording.

On each collection day, the cough count, the actual cough monitoring duration (in hours), and the coughs per hour will be derived for the total 24-hour period, the awake period, and the sleep period, respectively.

The percent change in 24-hour coughs per hour is defined as below:

Percent change in 24-hour cough frequency =

$$\left[\frac{(\text{Change from baseline in 24-hour cough frequency} \times 100)}{(\text{Baseline 24-hour cough frequency})} \right]$$

The proportion of participants with $\geq 30\%$ of reduction from baseline in 24-hour cough frequency is the number of participants with $\leq -30\%$ change in 24-hour cough frequency divided by the total number of participants with available data.

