- Proportion of subjects with $\geq 30\%$ reduction in awake objective cough frequency per hour at Week 12
- Change from baseline in Cough Severity Visual Analog Scale (VAS) at Week 12

Other Secondary

- Change from baseline in 24-hour objective cough frequency after 4 and 8 weeks (Day 28 and 56) of treatment
- Change from baseline in awake objective cough frequency after 4 and 8 weeks (Day 28 and 56) of treatment
- Change from baseline in 24-hour objective cough frequency at the Follow-Up visit (Day 112)
- Change from baseline in sleep objective cough frequency after 4, 8 and 12 weeks (Day 28, 56 and 84) of treatment
- Change from Baseline in Cough Severity Visual Analog Scale (VAS) at Weeks 4 and 8
- Change from Baseline in Leicester Cough Questionnaire (LCQ) individual Domain and Total scores
- Patient's Global Impression of Change (PGIC)
- Clinician's Global Impression of Change (CGIC)

Statistical approaches for analysis of the secondary endpoints will be detailed in the SAP. The continuous secondary efficacy endpoints will be analyzed using the same MMRM model as used for the primary efficacy analysis.

The categorical secondary efficacy endpoints will be analyzed using the stratified Miettinen and Nurminen (M&N) method, adjusting for gender and country.

Table 2 Analysis Strategy for Primary and Key Secondary Efficacy Endpoints

Endpoint	Statistical Method	Analysis Population	Missing Data Approach
Primary Efficacy Endpoint			
Change from baseline in 24-hour objective cough frequency after 12 weeks (Day 84) of treatment	MMRM	FAS	Observed data only
			Reference-based imputation & Tipping-point approach
Key Secondary Efficacy Endpoints			
Change from baseline in awake objective cough frequency after 12 weeks (Day 84) of treatment	MMRM	FAS	Observed data only
Proportion of participants with $\geq 30\%$ reduction in 24-hour objective cough frequency after 12 weeks (Day 84) of treatment	Stratified Miettinen and Nurminen (M&N)	FAS	Observed data only
Proportion of participants with $\geq 30\%$ reduction in awake objective cough frequency after 12 weeks (Day 84) of treatment	Stratified Miettinen and Nurminen (M&N)	FAS	Observed data only
Change from baseline in VAS after 12 weeks (Day 84) of treatment	MMRM	FAS	Observed data only

MMRM = Mixed Model Repeated Measures; GLMM= Generalized Linear Mixed Model; VAS = Visual Analogue Scales; FAS = Full Analysis set;

8.9.4 *Multiplicity Adjustment*

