## 6.0 ANALYSIS SETS

### 6.1 Full Analysis Set (FAS)

All randomized subjects who have taken at least one dose of study medication and provided at least one baseline and at least one post-baseline primary endpoint observation during the treatment period. Participants will be analyzed according to the treatment group to which they are randomized.

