### 8.1 General Analysis Considerations

For continuous variables, descriptive statistics will include the number of subjects reflected in the calculation (n), mean, standard deviation, median, minimum and maximum. Categorical variables will be summarized using frequency counts and percentages. Treatment differences in response rates (e.g., proportion of cough frequency responders) will be estimated using the stratified Miettinen and Nurminen (M&N) method (stratified by country and sex). Treatment differences in continuous data collected over multiple study visits (e.g., changes from baseline in awake cough frequency) will be assessed using the MMRM model with treatment, visit (nominal time point), country, sex, and the visit by treatment interaction as fixed effects, and baseline value as covariates.

Individual subject data obtained from the electronic case report forms (eCRFs), central laboratory, cough monitoring data, diary data, and any derived data will be presented by subject in data listings to facilitate the investigation of tabulated values and to allow for the clinical review. In general, all tables will be presented by treatment group and listings will be displayed by sorted unique subject identifier and treatment group. A subject identification number is defined as a 3-digit site number followed by a 3-digit sequentially assigned subject id (xxx-xxx). The treatment group in the listings will be based on the planned treatment(s) as allocated by the randomization scheme.

All p-values will be rounded to 4 decimal places. If a p-value is less than 0.0001 it will be displayed as “< 0.0001”, a p-value rounding to 1 will be displayed as “> 0.9999”. Unless otherwise specified all summaries will be performed by treatment group, all efficacy analyses will be based upon the FAS and all safety analyses will be based upon the Safety Analysis Set. Demographic and baseline characteristic analyses will be based upon the FAS, Safety All Randomized Subjects. The safety and demographic tables will include a total column along with the treatment columns.

The analyses described in this plan are considered a priori, in that they have been defined prior to database lock. Any analyses not described herein performed subsequent to database lock will be considered post hoc and exploratory.

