## 8.4 Data Handling Rules for Cough Analysis

The 24-hour cough frequency (coughs per hour) for a specified visit is calculated as:

$$\text{24-hour cough frequency} = \frac{\text{total number of cough events over 24-hour monitoring period}}{\text{Total duration (in hours) over 24-hour monitoring period}}$$

The awake cough frequency (coughs per hour) is defined as below:

$$\text{Awake cough frequency} = \frac{\text{total number of cough events during the monitoring period the subjects is awake}}{\text{Total duration (in hours) for the monitoring period the subject is awake}}$$

Awake duration (hours) is time between waking up and sleep during the 24-hour monitoring period.

The cough data will contain all cough events occurring during that 24-hour monitoring period as well as the information about “sleep time” and “awake time”. Any session with duration of

recording < 4 hours will be considered as missing. Repeated monitoring may be conducted when there is an equipment failure or an unacceptable evaluation from the initial monitoring.

In general, each 24-hour session is composed by an awake monitoring period and a sleep monitoring period. If a subject did not wake up before the end of the recording session, it will be assumed that the subject slept for the rest of the session. The session will have missing awake time, and the rest of session will be considered under the sleep monitoring period. For any session with both sleep time and awake time missing, the entire 24-hour session will be considered under the awake monitoring period, unless the session has early termination of recording.

On each collection day, the cough count, the actual cough monitoring duration (in hours), and the coughs per hour will be derived for the total 24-hour period, the awake period, and the sleep period, respectively.

The percent change in 24-hour coughs per hour at each specific visit is defined as below:

percent change in 24-hour cough frequency =

$$[(\text{change from baseline in 24-hour cough frequency} \times 100) / (\text{baseline 24-hour cough frequency})]$$

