## 8.7 Multiplicity Adjustments

The study is designed to evaluate the efficacy profile of serlopitant 5 mg versus placebo. The sequential testing procedure will be employed to control the overall Type I error rate at 5% with respect to multiple comparisons for the primary and key secondary endpoints. The hypothesis testing procedure will be done in a hierarchical order as specified below:

- H1: Change from baseline in 24-hour objective cough frequency after 12 weeks (Day 84) of treatment.
- H2: Change from baseline in awake objective cough frequency after 12 weeks (Day 84) of treatment
- H3: Proportion of subjects with  $\geq 30\%$  reduction in 24-hour objective cough frequency per hour at Week 12 (Day 84)
- H4: Proportion of subjects with  $\geq 30\%$  reduction in awake objective cough frequency per hour at Week 12 (Day 84)
- H5: Change from Baseline in cough severity visual analog scale (VAS) at Week 12 (Day 84)

First, the test ranked as first will be tested and the difference will be declared statistically significant if the one-sided p value is less than 0.05. Second, in case that the difference for the first comparison is statistically significant, the comparison ranked as second will be tested, and the difference will be declared statistically significant if the one-sided p-value is less than 0.05. The testing will continue as long as the previously ranked objective was statistically significant.

All other efficacy variables will be tested at the 0.05 level of significance without multiplicity adjustment.

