## 9.6 Efficacy Analyses

For efficacy endpoints, the analysis on FAS will be considered as the primary analysis.

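### Analysing VAS (H5), LCQ, PGIC and CGIC only in subjects with a usable baseline and at least one usable on-treatment cough recording drops valid ratings; a set per instrument would keep them

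*Protocol*

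**What the plan says.** **The set.** The protocol (synopsis and 8.4) limits the FAS to randomised, dosed subjects who "provided at least one baseline and at least one post-baseline primary endpoint observation during the treatment period". SAP 6.1 repeats it: "All randomized subjects who have taken at least one dose of study medication and provided at least one baseline", plus a post-baseline primary endpoint value on treatment. The primary endpoint is 24-hour cough frequency, so both conditions are about cough recordings.

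**Where it is used.** SAP 8.1 states that "all efficacy analyses will be based upon the FAS", and SAP 9.6 that "For efficacy endpoints, the analysis on FAS will be considered as the primary analysis". Protocol Table 2 (section 8.9.3) assigns the row "Change from baseline in VAS after 12 weeks (Day 84) of treatment" to the FAS, and SAP 8.7 lists that endpoint as H5, last in the alpha-controlled hierarchy. No other set is named for VAS, LCQ, PGIC or CGIC.

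**What counts as a recording.** Protocol 8.3: "Any session with duration of recording < 4 hours will be considered as missing". SAP 8.4 adds: "Repeated monitoring may be conducted when there is an equipment failure or an unacceptable evaluation from the initial monitoring". SAP Appendix C provides repeat labels for every monitoring visit, including baseline, and keeps the repeat records in the analysis data.

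**How the other instruments are collected.** Protocol Table 4 lists VAS, LCQ and PGIC as paper instruments. The investigator completes the CGIC at Day 85/ETD (protocol 6.5.9). That visit collects VAS, LCQ, PGIC and CGIC. Protocol Tables 3 and 4 schedule monitors only at Baseline and Days 28, 56, 84 and 112.

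**The concern.** Entry to the analysis of four instruments depends on the success of a fifth that they do not use. The filter has no function for them. Inclusion criterion 5 requires a baseline VAS score, so every eligible randomised subject has one. LCQ is scheduled on Day 0. PGIC and CGIC measure change directly and need no baseline value.

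Two things are at stake. One is precision, for H5 and for LCQ, which is tied to a stated objective. The other is selection after randomisation: a subject who stops before any on-treatment recording leaves the efficacy set altogether, although SAP 9.6.4.4 and 9.6.4.5 plan to analyse PGIC and CGIC at Day 85/ETD. Protocol 5.6 lists likely drug-related adverse events of Grade 2 or higher among the reasons for stopping, so this loss can differ between arms.

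**Working it through.** **1. The plan's own sample size.** Inputs (protocol 8.1): ratio 0.75, CV 0.64, one-sided alpha 0.05, power 90%, dropout 15%.

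- Log-scale SD = sqrt(ln(1 + 0.64²)) = 0.5859; effect = |ln 0.75| = 0.2877.
- n per arm = 2 × ((1.6449 + 1.2816) × 0.5859 / 0.2877)² ≈ 71.05, so 72. An exact noncentral-t calculation also gives 72 (power 0.901).
- 72 / 0.85 = 84.7, so 85 per arm and 170 in total. The stated figure reproduces and is not affected by this point.

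**2. Who is excluded.**

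| Situation of a dosed subject | In the FAS? | Consequence for the other instruments |
|---|---|---|
| One or two on-treatment sessions fail, the rest usable | Yes | None |
| Session stops early but lasts 4 hours or more | Yes | None |
| Baseline session unusable, recovered by a repeat | Yes | None |
| Baseline session unusable, not recovered | No | VAS, LCQ, PGIC and CGIC all lost |
| No usable session at Days 28, 56 or 84 | No | All lost |
| Stops before Day 28, ETD visit attended, no recording made | No | ETD LCQ, PGIC and CGIC lost; an ETD VAS is not a Day 28, 56 or 84 value, so H5 is little affected |

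**3. Device route.** Let q be the chance that a scheduled session yields no usable recording after any repeat. It is assumed, and taken as independent between sessions. Share excluded = 1 − (1 − q)(1 − q³).

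| q (assumed) | Excluded, of 170 | of which all three on-treatment sessions failed | Subjects with any failed session of four | Excluded as share of those |
|---|---|---|---|---|
| 2% | 3.4 | 0.001 | 13.2 | 26% |
| 5% | 8.5 | 0.02 | 31.5 | 27% |
| 10% | 17.2 | 0.15 | 58.5 | 29% |

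Nearly all device exclusions therefore come from the baseline session. That session is recorded on Day 0 after randomisation and collected on Day 1 before the first dose (protocol 6.5.3 and 6.5.4).

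**4. Early-stop route.** 15% of 170 = 25.5 dropouts. Spread evenly over 84 days (assumed), 28/84 of them stop before Day 28: 25.5 / 3 = 8.5 subjects. No device fault is needed. How many attend the ETD visit is not given, so 8.5 is an upper figure for ratings lost this way under that assumption.

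**5. Precision.** Let f be the share of subjects with VAS data but outside the FAS (assumed). SE increase = 1/sqrt(1 − f) − 1. Power, starting from an assumed 90%, = Φ((1.2816 + 1.6449) × sqrt(1 − f) − 1.6449).

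| f | Subjects of 170 | SE increase | Power |
|---|---|---|---|
| 2% | 3.4 | 1.0% | 89.5% |
| 5% | 8.5 | 2.6% | 88.6% |
| 10% | 17 | 5.4% | 87.1% |

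An exact t calculation starting from 72 per arm and 90.1% power gives 89.6%, 88.7% and 87.2%.

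**The case against.** The plan anticipates recorder failure. Sessions of 4 hours or more count, repeats are allowed (including at baseline), and one usable session out of three keeps a subject in. A reader might infer from the FAS wording that questionnaire data are thrown away whenever a recorder fails. The documents do not support that: in step 3 only about 26% to 29% of subjects with any failed session would be excluded.

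A reader might also infer that recorder failure biases the comparison. For the baseline session it cannot do so through drug effect, because the recording is finished before the first dose and under double blinding. Nothing in the documents shows that subjects refuse or remove the recorder in relation to benefit.

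H5 is powered nowhere in the documents, is tested only if H1 to H4 all succeed, and is barely touched by early stopping. A single set also keeps H1 to H5 on one population. Any set that needs a post-baseline value still selects after randomisation.

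All of this stands, and it limits the point to a minor one. It does not remove it. Repeats are optional and appear only in the SAP. The protocol takes baseline as the last value before treatment starts, so a repeat rescues the baseline only if made before dosing, and the protocol sets no check of the recording before that dose. The early-stop route is untouched by these safeguards. A set based on each instrument's own data still requires a value, but only one that its analysis needs.

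**Conclusion.** The mismatch is certain from the text: recording-based entry governs four instruments that do not use the recorder. Its size is unknown, because the documents give no recorder failure rate, no timing of dropout and no VAS effect or SD. On assumed losses of 2% to 10%, H5 would lose 0.5 to 2.9 percentage points from an assumed 90% power. That is a loss of precision; the documents do not support calling it a bias in H5. The clearer selection issue lies with LCQ, PGIC and CGIC in subjects who stop before Day 28, up to about 8.5 of 170 under even dropout. Those three endpoints are tested without multiplicity adjustment. H1 to H4 and the sample size of 170 are unaffected. Minor severity; a cheap improvement.

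**What to change.** Amend protocol 8.4 and Table 2, and SAP 6.1 and 8.1, before unblinding:

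- **Cough-recording endpoints:** keep the current FAS.
- **VAS and LCQ:** analyse, as randomised, all randomised and dosed subjects with that instrument's own baseline and at least one post-baseline value in the treatment period, counting Day 85/ETD for LCQ.
- **PGIC and CGIC:** analyse, as randomised, all randomised and dosed subjects with a rating.

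The cost is wording in two documents and one population flag per instrument. No new data are needed. The drawback is that n will differ slightly between endpoints, which a line in each table can explain.
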